5.9.3 Code Breaks

Since the investigator is un-blinded to the treatment there will be no requirement of breaking the code in the study by/for investigator.

 GlaxoSmithKline	Document Name	Clinical Study Protocol 204477		
	Type	Version	Document Identifier	Effective Date
	eldo_clinical_doc	5.0; Most-Recent; Effective; CURRENT	090032d580daa95e	10-Oct-2017 06:16:49
	Reason For Issue	Auto Issue		

5.10. Packaging and Labelling

The test product will be supplied in plain white sachets with a study label affixed to each sachet. Each subject will receive a subject carton with sufficient sachets to cover the duration of the intervention period.

The contents of the label will be in accordance with all applicable regulatory requirements and will be the responsibility of the Clinical Supplies Department, GSKCH.

All sundry items will be supplied in their commercial packaging for use throughout the study as required.

Care should be taken with the supplied products and their labels so that they are maintained in good condition. It is important that all labels remain intact and legible for the duration of the study. Participants should be instructed to not remove or deface any part of the study label.

5.10.1. Accountability of Product

All products supplied are for use only in this clinical study and should not be used for any other purpose.

The investigator or designee will maintain a full record of test product accountability. A Product Dispensing Log must be kept current and will contain the following information:

- The identification of the subject to whom the test product was dispensed.
- The dates and quantity of the test product dispensed to the subject.
- The dates and quantity of the test product/empty sachets returned by the subject (if applicable).

The inventory must be available for inspection by the study monitor during the study. During and at the end of the study, test product supplies will be verified by the monitor. Test product supplies will then be either collected by the study monitor or returned by the investigator or designee to the GSKCH Clinical Supplies Department or designated vendor.

	Document Name	Clinical Study Protocol 204477		
	Type	Version	Document Identifier	Effective Date
	eldo_clinical_doc	5.0; Most-Recent; Effective; CURRENT	090032d580daa95e	10-Oct-2017 06:16:49
	Reason For Issue	Auto Issue		

5.10.2. Storage of Product

Study product supplies must be stored in compliance with the label requirements in a secure place with limited or controlled access.

6. STUDY ASSESSMENTS AND PROCEDURES

This section lists the procedures and parameters of each planned study assessment. The exact timing of each assessment is listed in the Schedule of Events section.

Adherence to the study design requirements, including all assessments and procedures are essential and required for study conduct.

6.1. Matched Pair Formation

Each school will be deemed as a cluster. Schools with following characteristics will be invited to participate in the study:

- ~~Located in peri-urban areas~~
- No government or sponsored micronutrient supplementation scheme running in past 6 months
- Mixed-gender education/co-education system of education
- No history of any outbreak or clustering of cases of infectious diseases in last month

Schools which agree to participate will be selected and will be subsequently matched for cluster size (in context to the number of children in 7-10 yrs age group), socioeconomic profiles of students, and type of school; government subsidised or private.

6.2. Informed Consent and Assent

The investigator, or designee, must obtain written (signed and dated) informed consent from each participant's parent *or* LAR and/or impartial witness, participating in this study after adequate explanation of the aims, methods, objectives, and potential hazards of the study. The investigator, or designee, must also explain to the participant's parents or participant's LAR that they are completely free to refuse for their child to enter the study or to withdraw from it at any time. They will also be notified that they are free to withdraw consent for a collected biological sample to be

 GlaxoSmithKline	Document Name	Clinical Study Protocol 204477		
	Type	Version	Document Identifier	Effective Date
	eldo_clinical_doc	5.0; Most-Recent; Effective; CURRENT	090032d580daa95e	10-Oct-2017 06:16:49
	Reason For Issue	Auto Issue		

used after the collection. The investigator may contact the parents/LARs during parents-teachers meeting to inform them about the study. Consent will be obtained from interested parents/LARs on the same day of parents-teachers meeting if possible or they will be provided with alternate appointment dates to come for consenting and screening activities.

Once the parental or LAR consent process is over, separate assent will be obtained from the prospective study participants, whose parents/ LARs have consented. If participants do not give assent despite parental/LAR consent, they will be excluded from the study. Assent will always be obtained only after consent is obtained from Parents/LAR.

Appropriate forms for documenting a written consent and assent-will be provided by the investigator or by GSKCH or by CRO. The investigator, or designee, should sign and date the consent and assent-form to confirm that the process was completed correctly.

A copy of the signed and dated consent and assent-forms will be provided to the participant's parents / LARs along with any other written information and they will be instructed to retain these documents.

Obtaining informed consent and assent and performing screening activities can be on different dates but informed consent and assent will be obtained prior to performing and applying any screening criteria or procedures. Screening activities should be within 60 days of obtaining consent-and assent. A participant will be considered to be enrolled in the study after obtaining consent and assent, he/she has been found eligible for study basis all study screening criteria and procedures.

If, during a participant's participation in the study, any new information becomes available that may affect the participant's/parents or LARs willingness to participate in the study, each ongoing participant's parent or LAR should receive a copy of this new information and be re-consented into the study. Re-assent will also be sought from participants Participant's parents or LAR should be provided with a copy of the signed and dated amended consent and assent-form.

6.3. Demographics

The following demographic parameters will be captured by the Investigator or designee and recorded on the CRF: year of birth, gender and race.

 GlaxoSmithKline	Document Name	Clinical Study Protocol 204477		
	Type	Version	Document Identifier	Effective Date
	eldo_clinical_doc	5.0; Most-Recent; Effective; CURRENT	090032d580daa95e	10-Oct-2017 06:16:49
	Reason For Issue	Auto Issue		

6.4. Medical History and Concomitant Medication

For each participant, the medical history will be taken and reviewed by the Investigator or medically qualified designee. Details of any relevant medical or surgical history (in the last six months), including allergies or drug sensitivity, will be recorded. Any concomitant therapy taken in the 30 days prior to the Screening Visit and throughout the study will also be recorded.

6.5. General Physical Examination

The Investigator or their designee will perform a physical examination which should include assessment of the following body systems as appropriate: Central Nervous System (CNS); eyes; ears, nose and throat (ENT); respiratory; cardiovascular; GI; musculoskeletal; neurological; endocrine/metabolic; haematopoietic/lymphatic; dermatological.

The outcome of these assessments will be documented in the CRF and any abnormalities will be described. The Investigator can interpret individual findings based on the participant's age, physical state and level of fitness. Participants with clinically significant findings outside the normal range should be excluded from the study based on investigator's discretion. This decision will be documented on the Comments page of the CRF.

6.6. Vital Signs

Qualified site staff will record participant's heart rate and oral body temperature when participants are resting in a sitting position, checked against the following normal ranges (which are given as a guide) and recorded in appropriate forms.

Heart rate:

70-110 beats per minute.

Oral body Temperature:

97.7–99.5 °F

The Investigator can interpret individual findings based on the participant's age, physical state and level of fitness. Participants with clinically significant readings outside the normal range should be excluded from the study based on investigator's discretion. This decision will be documented on the Comments page of the eCRF.

 GlaxoSmithKline	Document Name	Clinical Study Protocol 204477		
	Type	Version	Document Identifier	Effective Date
	eldo_clinical_doc	5.0; Most-Recent; Effective; CURRENT	090032d580daa95e	10-Oct-2017 06:16:49
	Reason For Issue	Auto Issue		

6.7. Anthropometric Measurements (Height, Weight, BMI and HAZ)

All anthropometric measurements will be performed using the guidelines adopted at the National Institute of Health sponsored Arlie Conference [Anthropometric Reference Manual, 1988].

Height will be measured using a portable stadiometer (SECA 213), with the subject standing bare-foot, to the nearest 0.1 cm. An average of 3 measurements will be recorded.

Weight will be measured in standard clothing on standardised weighing scale (SECA 874) to the nearest 0.1 kg. Weight will be measured in the unit kg and an average of 3 measurements will be recorded.

BMI will be calculated using the following formula:

$$\text{BMI} = \text{Weight}_{\text{kg}} / (\text{Height}_{\text{m}})^2$$

HAZ will be obtained using the World Health Organisation (WHO) Anthroplus software available at <http://www.who.int/growthref/tools/en/> (WHO AnthroPlus for personal computers Manual: Software for assessing growth of the world's children and adolescents. Geneva: WHO, 2009).

6.8. Hb Assessment

A non-invasive spectrophotometry based instrument (Masimo Pronto 7 Pulse CO-Oximeter) will be used for Hb assessment. The Masimo Pronto 7 Pulse CO-Oximeter uses signal extraction technology pulse oximetry.

Site staff will select an appropriate sized sensor. The sensor will be placed on the nail of ring finger of the left hand, followed by assessment of haemoglobin by pressing the test button. Appropriate care will be taken by the site staff to ensure that the participant's test finger nail does not contain any nail paint.

6.9. Collection, Storage, Assessment and Destruction of Human Biological Samples

Human biological samples will be collected with prior consent (from parents/LARs) and assent (from participants) as per the study schedule.

 GlaxoSmithKline	Document Name	Clinical Study Protocol 204477		
	Type	Version	Document Identifier	Effective Date
	eldo_clinical_doc	5.0; Most-Recent; Effective; CURRENT	090032d580daa95e	10-Oct-2017 06:16:49
	Reason For Issue	Auto Issue		

All collected samples will be coded with unique identifiers and tracked until destruction. Samples must be clearly labeled with the screening number, protocol number, site/centre number, and visit date. Under no circumstances should a collected sample be left unidentified. Details for the preparation and shipment of samples will be provided in the laboratory manual.

~~Samples will be stored in requisite storage conditions mentioned for respective samples. Samples will be processed and shipped to laboratory as per details mentioned in the laboratory manual.~~

IMMEDIATELY AFTER COLLECTION, SAMPLES WILL BE FROZEN AT OR BELOW -20°C. IF FREEZING IS NOT POSSIBLE, THEY WILL BE REFRIGERATED IMMEDIATELY AT 2-8°C AND MAINTAINED AT THIS TEMPERATURE FOR NO LONGER THAN 4 HOURS, BEFORE SERUM SEPARATION AND SUBSEQUENT FREEZING AT OR BELOW -20°C. SAMPLES IF STORED FOR A PERIOD BEYOND EXPIRY OF STABILITY AT -20°C SHOULD BE FROZEN AT OR BELOW -70°C.

ALL SAMPLES (BASELINE AND END-LINE) WILL BE ANALYSED IN BATCHES, IN PERIODICITY BASED ON THEIR STABILITY AT -20 °C OR -70 °C (IF STORED FOR A PERIOD BEYOND EXPIRY OF STABILITY OF SAMPLES AT -20° C).

HBS TO BE STORED TILL IT IS PROPERLY DISPOSED OF AT THE END OF ITS RETENTION PERIOD (I.E. TILL STUDY REPORT IS ISSUED), OR USEFUL LIFE (I.E. TILL EXPIRY OF STABILITY AT -70°C), OR UPON RECEIPT OF A REQUEST TO DESTROY THE HBS DUE TO WITHDRAWAL OF CONSENT. NO SAMPLE WILL BE RETAINED BEYOND 1 YEAR FROM LAST PARTICIPANT LAST VISIT.

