After application of an anesthetic patch/ointment **E.G. LIDOCAIN, TETRACAIN ETC** to reduce discomfort, a total volume of approximately 7 mL (each at ~~screening and~~ baseline visit **AND END OF STUDY VISIT**, total of approximately 14 mL) of whole blood will be collected from each participant by a certified phlebotomist for biochemical and micronutrient analysis.

The participant will be made to **LIE DOWN ON BED** or sit comfortably on a chair with his arm stretched on the table. He/she will be asked to exercise the arm so as to make the ante-cubital vein prominent. A tourniquet will be tied about 2 inches above the vein on the upper arm. The vein will be palpated, and the area will be sterilised. The vein will be pricked and vacutainer placed in position to collect sample. Blood samples will be collected in ~~single vial (7 ml each)~~ **TWO VIALS (3.5 ML EACH)** by designated staff.

~~After collection, all blood samples will be coded and refrigerated immediately at temperature ≤ 4°C and will be maintained at this temperature for no longer than 24 hours (ideally less than 2 hours). At the laboratory, these samples will be converted into serum and then preserved in aliquots at ≤ -20 °C, until further required analyses are performed.~~

 GlaxoSmithKline	Document Name	Clinical Study Protocol 204477		
	Type	Version	Document Identifier	Effective Date
	eldo_clinical_doc	5.0; Most-Recent; Effective; CURRENT	090032d580daa95e	10-Oct-2017 06:16:49
	Reason For Issue	Auto Issue		

~~All samples (baseline and end line) will be analysed in batches, in periodicity based on their stability data at 20 °C.~~

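### The merged storage rule in protocol 6.9, read literally, freezes blood before serum is separated, which conflicts with the serum endpoints

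*Protocol*

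**What the plan says.** Protocol 6.9 sets the storage rule for all human biological samples. It gives the default and then the alternative: "IMMEDIATELY AFTER COLLECTION, SAMPLES WILL BE FROZEN AT OR BELOW -20°C. IF FREEZING IS NOT POSSIBLE, THEY WILL BE REFRIGERATED IMMEDIATELY AT 2-8°C". The alternative continues "AND MAINTAINED AT THIS TEMPERATURE FOR NO LONGER THAN 4 HOURS, BEFORE SERUM SEPARATION AND SUBSEQUENT FREEZING AT OR BELOW -20°C". The default makes no exception for blood and has no serum step. The section also says "Details for the preparation and shipment of samples will be provided in the laboratory manual".

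Protocol 6.9.1.3 covers blood. At baseline and at end of study, about 7 mL "of whole blood will be collected from each participant by a certified phlebotomist for biochemical and micronutrient analysis", into "TWO VIALS (3.5 ML EACH) by designated staff". No current text in 6.9.1.3 says what happens to the tubes next. The deleted text there refrigerated the blood and continued: "At the laboratory, these samples will be converted into serum and then preserved in aliquots".

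Protocol 6.9.1.1 (urine) still tells staff to keep specimens refrigerated or in a cooler until they reach the laboratory. Protocol 6.9.2 lets laboratory assessments follow either the laboratory manual or the protocol's own laboratory section.

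SAP 4.4.2 analyses nine micronutrients under a heading that names a blood sample. It analyses ferritin, sTfR, CRP and AGP as serum parameters.

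**The concern.** The only current protocol instruction to separate serum sits inside the branch that applies when freezing cannot be done. A school with a freezer that follows the rule puts whole blood straight into it and never reaches that instruction. The analyses that follow assume serum.

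The laboratory values also have several uses. They are the change-from-baseline outcomes for two secondary objectives. CRP and AGP are covariates in the ferritin and sTfR model. The micronutrients enter the correlations with gut integrity (SAP 4.6), and laboratory results are compared with reference ranges in the shift tables (SAP 4.7.2). The SAP has no provision for specimens of differing matrix. A baseline sample cannot be taken again once the intervention has started.

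**Working it through.** No sample-size, power or alpha formula applies, because protocol 9.1 sizes the trial on the primary endpoint alone. The check is a reading of the current, unstruck text, plus a count of analytes.

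1. **Does the rule in 6.9 cover blood?** Yes. It refers to samples without qualification, and its fallback branch mentions serum, which only blood yields. The default therefore cannot be read as confined to urine and saliva.

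2. **The two branches side by side.**

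| Step | Default (6.9) | Fallback (6.9) |
|---|---|---|
| First action | Freeze at or below -20°C | Refrigerate at 2-8°C, at most 4 hours |
| Serum separation | Not mentioned | Before freezing |
| Final state of blood, read literally | Frozen unseparated | Frozen serum |

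3. **Does any other current text supply the missing step?** 6.9.1.3 does not, because all its handling text after collection is struck. 6.9.2 does not describe processing. The laboratory manual may, but it was not among the documents.

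4. **How the rule probably arose.** The deleted urine and saliva text in 6.9.1.1 and 6.9.1.2 had the same freeze-first, refrigerate-otherwise structure. The deleted blood text refrigerated, made serum, then froze. Merging the three appears to have carried the urine and saliva default over to blood. This is context only; the finding rests on the current text.

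5. **Analytes drawn from these tubes.** Vitamins A, B12, D, E and folate (5) + selenium, zinc, copper and iron (4) + ferritin, sTfR, CRP and AGP (4) = 13. Vitamins B6 and C still appear in places in the protocol, but Amendment 10 dropped them and the SAP does not analyse them. The SAP calls 4 of the 13 serum parameters. For the other 13 - 4 = 9, serum is implied by the fallback branch in 6.9.

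6. **Samples affected.** Neither document says which schools can freeze on site, so the share taking the default is anywhere from 0% to 100%.

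7. **If the branch varied by school.** SAP 3.3 gives four schools, two per product group. The ANCOVA has product group as a fixed effect and school as a random effect. Four school means less two group means leave 4 - 2 = 2 between-school degrees of freedom. If both schools in one arm froze and both in the other refrigerated, branch and product group would be identical and no model could separate them. If the split were not exact, adjusting for branch would leave 2 - 1 = 1 degree of freedom.

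**The case against.** The strongest defence is that 6.9 is not the whole instruction. It leaves preparation details to the laboratory manual, and making serum is the kind of detail a manual holds. The Schedule of Events lists serum ferritin. The amendment log, as context, describes up to 4 hours at 2-8°C as the more appropriate initial storage and mentions centrifugation of blood. On this view, three rules were merged clumsily and nobody intended to freeze whole blood.

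Much of that stands as an account of intent. It does not repair the text. A manual that requires separation first would contradict an explicit protocol default, and 6.9.2 gives the manual no precedence. Staff would have to depart from one document to follow the other.

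Three stronger inferences are not supported:

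- **That blood will in fact be frozen whole.** The manual is unseen, and the cooler-and-transport text still standing in 6.9.1.1 suggests that at least some specimens leave the school unfrozen.
- **That no valid serum can be recovered for any of the 13 analytes.** Neither document has data on how freezing whole blood affects any of them, and only four are named as serum.
- **That a false product effect will appear.** Nothing shows that schools differ in freezing capacity. If each school used one branch at both visits, a constant additive shift would also cancel from the raw change. It would cancel from the baseline-adjusted comparison only if the slope of change on baseline were zero.

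**Conclusion.** The point holds as a conflict in the current text. The default in 6.9, followed literally, freezes blood before serum separation, while the SAP analyses four analytes as serum and serum is implied for nine more. This is a stated rule that leads to the wrong specimen, so it is more than missing detail.

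Its reach is limited. All 13 blood analytes are exposed, at both visits, for any child whose blood took the default branch, but the number of such children cannot be determined without the laboratory manual and site records. Confounding with product group is conditional on schools having used different branches. The primary endpoint (physician-diagnosed ill days), its analysis and the sample size do not depend on these samples.

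**What to change.** Amend 6.9 so that the immediate-freezing default does not apply to blood. State that, at every school and at both visits, blood is held at 2-8°C, serum is separated within the 4-hour limit the section already gives, and only serum is frozen at or below -20°C. In the same amendment, reconcile 6.9 with 6.9.1.1 (refrigeration until transport), 6.9.1.3 (no processing step left) and the laboratory manual, so that each specimen type has one sequence.

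If blood has already been collected, document which branch was used at each school and visit and report it with the biomarker results.

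Haemolysis may be recorded as a laboratory flag. It should not become a reason for excluding data unless the criterion is set in advance and applied without knowledge of product group, because in an open-label trial an undefined exclusion adds a discretionary choice.

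The cost is a wording amendment and a check of the manual. The cold-hold window and the separation step are already in 6.9, but schools that had planned to freeze blood on site would have to arrange separation within 4 hours. No visit, blood volume or sample-size figure changes.

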6.9.1. Collection and Storage of Human Biological Samples

6.9.1. 1. Urine Samples

Urine samples will be collected for Lactulose:Mannitol test and Urinary Neopterin test.

For Urinary Neopterin test, spontaneous random urine will be collected. As this test does not require any solution to be administered, urine sample for this test will be collected prior to administration of Lactulose/Mannitol solution.

 GlaxoSmithKline	Document Name	Clinical Study Protocol 204477		
	Type	Version	Document Identifier	Effective Date
	eldo_clinical_doc	5.0; Most-Recent; Effective; CURRENT	090032d580daa95e	10-Oct-2017 06:16:49
	Reason For Issue	Auto Issue		

A urine volume of 2mL per participant will be stored in ~~coded cryovials~~ **CONICAL BOTTOM TUBES** and then will be transferred to laboratory and stored under ~~80°C~~ for further analysis.

For Lactulose:Mannitol test, The Lactulose-Mannitol solution to be used includes 250 mg/mL of lactulose and 50 mg/mL of mannitol (1002 mOsm/L), and will be administered at a dose of 2 mL/kg up to a maximum of 20 mL. All urine passed over duration of 2 ½ hours [Akram S *et al.*, 1998, Sequeira IR *et al.*, 2014] will be collected after administration of Lactulose:Mannitol solution. A prior 3 hours fasting is essential before administration of test solution. Participants will be allowed to return to their regular diet 30 minutes after ingestion of the lactulose:mannitol test solution. During the 2 ½ hour time, participants will be offered liquids frequently in order to permit collection of an adequate volume of urine. The start and stop time for the 2 ½ hour duration will be recorded for each participant. After 2 ½ hour urine collection total urine volume will be measured and recorded.

From the entire collection of urine in a container, 2 mL well mixed urine sample will be transferred in ~~coded cryovials~~ **RIA VIALS**. Remaining urine samples will be discarded as bio medical waste. The designated study staff will place all urine samples into a zip-lock bag containing absorbent toweling. All specimens will be refrigerated (or kept cold in a cooler with a frozen ice pack) until transported to the laboratory for analysis. The cooler will be securely sealed with tape and sent to the Laboratory, preferably on the same day as collection.

~~Immediately after collection, freeze samples at or below -20°C. If freezing is not possible, refrigerate immediately at 4°C and maintain at this temperature for no longer than 24 hours (ideally less than 2 hours) before freezing at or below -20°C.~~

~~All samples (baseline and end line) will be analysed in batches, in periodicity based on their stability data at -20 °C.~~

6.9.1. 2. Saliva Samples

Saliva sample will be collected for assessment of sIgA. Whole saliva is the gold standard when collecting oral fluid for biological testing. Since sIgA is location dependant [Beltzer, E.K. *et al.*, 2010] [Crawford, J.M *et al.*, 1975], whole saliva sample avoids localised secretions of specific salivary glands providing a more consistent specimen. Thus, saliva samples will be collected from each participant using passive drool method with Saliva Collection Aid (SCA) as described by the manufacturer) (Salimetrics, State College, PA).

 GlaxoSmithKline	Document Name	Clinical Study Protocol 204477		
	Type	Version	Document Identifier	Effective Date
	eldo_clinical_doc	5.0; Most-Recent; Effective; CURRENT	090032d580daa95e	10-Oct-2017 06:16:49
	Reason For Issue	Auto Issue		

Saliva will be collected using SCA. Ribbed-end of the SCA will be securely placed into a pre-labeled collection vial. Participants will be instructed to pool the saliva in mouth. SCA will be placed on mouth entry. Then, participants will be asked to tilt the head forward, and gently force saliva through the SCA into the vial to fill with at least 50 µL of volume. A small amount of air space will be reserved in the vial to accommodate liquid expansion during freezing. After collection of sample, SCA will be removed and discarded and cap will be attached to collection vial and tightened.

~~Immediately after collection, freeze samples at or below -20°C. If freezing is not possible, refrigerate immediately at 4°C and maintain at this temperature for no longer than 24 hours (ideally less than 2 hours) before freezing at or below -20°C. Samples if stored for more than 4 months should be frozen at -80°C.~~

~~All samples (baseline and end line) will be analysed in batches, in periodicity based on their stability at -20 °C (if stored for less than 4 months) or -80 °C (if stored for more than 4 months).~~

6.9.1. 3. Blood Samples

After application of an anesthetic patch/ointment **E.G. LIDOCAIN, TETRACAIN ETC** to reduce discomfort, a total volume of approximately 7 mL (each at ~~screening and~~ baseline visit **AND END OF STUDY VISIT**, total of approximately 14 mL) of whole blood will be collected from each participant by a certified phlebotomist for biochemical and micronutrient analysis.

The participant will be made to **LIE DOWN ON BED** or sit comfortably on a chair with his arm stretched on the table. He/she will be asked to exercise the arm so as to make the ante-cubital vein prominent. A tourniquet will be tied about 2 inches above the vein on the upper arm. The vein will be palpated, and the area will be sterilised. The vein will be pricked and vacutainer placed in position to collect sample. Blood samples will be collected in ~~single vial (7 ml each)~~ **TWO VIALS (3.5 ML EACH)** by designated staff.

~~After collection, all blood samples will be coded and refrigerated immediately at temperature ≤ 4°C and will be maintained at this temperature for no longer than 24 hours (ideally less than 2 hours). At the laboratory, these samples will be converted into serum and then preserved in aliquots at ≤ -20 °C, until further required analyses are performed.~~

 GlaxoSmithKline	Document Name	Clinical Study Protocol 204477		
	Type	Version	Document Identifier	Effective Date
	eldo_clinical_doc	5.0; Most-Recent; Effective; CURRENT	090032d580daa95e	10-Oct-2017 06:16:49
	Reason For Issue	Auto Issue		

~~All samples (baseline and end line) will be analysed in batches, in periodicity based on their stability data at 20 °C.~~

